7.2. Analyses

Demographics including geographic location, HCP specialty and prescribing/dispensing of POTIGA and other AEDs will be summarized using descriptive statistics for continuous data and proportions for categorical data.

The primary outcome is the proportion of HCPs answering each question of understanding of the risks associated with POTIGA correctly. Point estimates for the proportion with correct responses, and associated 95% confidence intervals, will be calculated for each question about the awareness of risks of POTIGA. In the case of multiple choice questions, the number and proportion of subjects reporting each response will also be provided.

GSK considers a proportion (%) of correct responses of at least 80% for each individual question to represent sufficient subject understanding of the risks associated with POTIGA. This is based on previous studies by GSK including the risk management program for LAMICTAL and TREXIMET. This threshold will be imposed for prescribers and pharmacists. Prescribers and pharmacists are the HCPs who will play an important role in re-enforcing the safety messages for POTIGA.

The proportion of correct answers to survey questions will be summarized overall and by demographic subgroups. Consideration of these subgroups may highlight differences in subjects' responses. Although the sample size in some subgroups may be relatively small and have low precision, data will be grouped into 2-3 sub-categories as appropriate to identify potential trends in subject understanding including:

- Demographics (geographic location)
- Type of HCP
- POTIGA prescribing/dispensing (yes or no, months prescribing POTIGA)
- Other practice/prescribing characteristics (years in practice, years prescribing AEDs, size of patient population)

This study is descriptive; hence there will be no formal statistical testing completed.

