8. PRECISION BY SAMPLE SIZE.....	16
9. STUDY LIMITATIONS.....	16
10. STUDY MANAGEMENT.....	17
10.1. Ethical approval and subject consent.....	17
10.2. Subject confidentiality	17
10.3. Reporting of adverse drug events	17
10.4. Study reporting and publications	17
11. APPENDICES	18
11.1. Screener.....	18
11.2. Questionnaire	23
11.3. GlaxoSmithKline Adverse Drug Reaction Form – Revised Nov 30, 2009	40

LIST OF ABBREVIATIONS

AE	Adverse Event
AED	Anti-epileptic drug
DHCP	Dear Healthcare Provider (Letter)
GSK	GlaxoSmithKline
HCP	Healthcare Provider
REMS	Risk Evaluation and Mitigation Strategy
US	United States

Trademark Information

Trademarks of the GlaxoSmithKline group of companies
POTIGA
LAMICTAL
LAMICTAL ODT
LAMICTAL XR
TREXIMET

Trademarks not owned by the GlaxoSmithKline group of companies
None

PROTOCOL SUMMARY

Rationale

As part of a post-marketing commitment, GSK will conduct a survey of prescribers' and pharmacists' understanding of the risk of urinary retention with POTIGA™ products. This is to address the effectiveness of the Risk Evaluation and Mitigation Strategy (REMS) as outlined in the REMS approved by the FDA on 10th June 2011.

Objective(s)

The objectives of this survey are to assess prescribers' and pharmacists' understanding of the risk of urinary retention and the symptoms of acute urinary retention potentially associated with POTIGA use as evaluated by a survey instrument.

Study Design

This is a cross-sectional study of approximately:

1. 200 physicians (e.g. neurologists/epileptologists/neurosurgeons) who have prescribed POTIGA at least once in the last 12 months.
2. 200 pharmacists who have dispensed an anti-epileptic drug (AED) at least once in the last 3 months.

Individuals eligible for the survey will be asked to take the survey online or via a telephone interview if the latter is preferred.

Study Endpoints/Assessments

The primary outcome of the survey is the proportion of physicians and pharmacists providing correct responses to a series of questions concerning the risk of urinary retention and the symptoms of acute urinary retention that may be associated with POTIGA. The risks captured will be those described in the POTIGA Dear Healthcare Provider (DHCP) letters, specifically risks of urinary retention.

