1. INTRODUCTION

POTIGA was approved with a FDA requirement for a Risk Evaluation and Mitigation Strategy (REMS). The goal of the REMS for POTIGA is to inform healthcare professionals of the risk of urinary retention and the symptoms of acute urinary retention in patients taking POTIGA. The REMS is comprised of a communication plan for healthcare professionals that is designed to disseminate information about the risk of urinary retention with POTIGA and highlight this potential risk and the need to inform patients to seek immediate medical attention for symptoms of urinary retention, inability to urinate, and/or pain with urination. There are two elements of the communication plan: (1) A Dear Healthcare Professional (HCP) Letter designed to disseminate information about the risk of urinary retention with POTIGA; letters are disseminated within 4 weeks of first retail availability (actual – May 7, 2012) and annually for the next two years (2) a REMS Program Website (available at time of launch; actual -April 16, 2012).

The target audience for these communications is: (1) Prescribing physicians i.e., Epileptologists, Neurologists and Neurosurgeons, (2) Pharmacists dispensing POTIGA tablets and the Medication Guide.

As a condition of approval, FDA requires that GlaxoSmithKline (GSK) assess the effectiveness of the communication plan. Accordingly, a survey will be conducted among a sample of prescribing physicians to evaluate whether they can recall the risk of urinary retention with POTIGA. In addition, the survey will evaluate where HCPs prefer to seek information for POTIGA, for example Dear HCP letters, website, or product labeling. The survey will concentrate on the risks described in the DHCP letter for POTIGA, though it is recognised that the DHCP letter is not the only source of information concerning risks associated with medication use. The design for this study is based on previous experience of risk management programs for GSK products.

A survey will also be conducted among a sample of pharmacists to evaluate whether they can recall the risk of urinary retention with POTIGA.

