2. OBJECTIVE(S)

The objectives of this study are:

1. To assess prescribers' understanding of the risk of urinary retention and the symptoms of acute urinary retention with POTIGA as evaluated by a survey instrument.
2. To assess pharmacists' understanding of the risk of urinary retention and the symptoms of acute urinary retention with POTIGA as evaluated by a survey instrument.

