3.3.1. Risk management studies for other GSK medications

Experience from previous risk management studies was used to determine the threshold for the proportion of correct responses per individual survey question against which to base sample size calculations and precision estimates.

The REMS post marketing commitments for LAMICTAL™ (NDA 022115) included:

- a. A survey of patients' understanding of the serious risks of Lamictal (lamotrigine) Orally Disintegrating Tablets
- b. A report on periodic assessments of the distribution and dispensing of the Medication Guide in accordance with 21 CFR 208.24
- c. A report on failures to adhere to distribution and dispensing requirements, and corrective actions taken to address noncompliance

The REMS post marketing commitments for TREXIMET™ (NDA 21-926) included:

- a. Survey of patients' understanding of the serious risks of TREXIMET;
- b. Report on periodic assessments of the distribution and dispensing of the Medication Guide in accordance with 21 CFR 208.24; and,
- c. Report on failures to adhere to distribution and dispensing requirements, and corrective actions taken to address non-compliance.

Based on these studies, a threshold of 80% was determined to be acceptable for the proportion of subjects answering correctly the questions regarding risks associated with POTIGA. This threshold will be imposed for prescribers and pharmacists, not urologists

nor emergency room doctors. Prescribers and pharmacists are the HCPs who will play an important role in re-enforcing the safety messages for POTIGA.

It should be noted that TREXIMET and POTIGA REMS have since been revised, because the FDA determined that a Medication Guide is not necessary to ensure the benefits of the drug outweigh the risks described above because labeling and a REMS that includes a communication plan will be adequate to describe these serious risks. The Medication Guide will be part of the approved labeling and be subject to the requirements under 21 CFR 208.

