5.2. Outcomes

Subject understanding of the risk of urinary retention and the symptoms of acute urinary retention associated with POTIGA will be assessed using the survey instrument.

The primary outcome of this study is the proportion of subjects that correctly respond to individual survey questions concerning the risk of urinary retention and the symptoms of acute urinary retention associated with POTIGA. The order in which potential responses to survey questions appear will be randomized. The proportion responding correctly will be tabulated separately for each item in the subject understanding survey instrument. These risks represent those described in the DHCP letter.

At the conclusion of the online survey, the final screen will display a summary of the relevant information from the POTIGA prescribing information, and a link to <http://www.potiga.com>. The phone respondents will be offered materials by email or the POTIGA website, but will also be given the toll-free number for the POTIGA response center [name] ([name]).

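### Section 7.2 reads 80% correct on each question as sufficient understanding of the risks, but no planned result shows how many respondents know the risk, the symptoms and the action together

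*Protocol*

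**What the plan says.** The objectives in protocol section 2 are to assess, in prescribers and in pharmacists, "understanding of the risk of urinary retention and the symptoms of acute urinary retention with POTIGA as evaluated by a survey instrument". Risk and symptoms are named together. Section 1 adds that the communication plan is meant to highlight "the need to inform patients to seek immediate medical attention for symptoms of urinary retention".

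The questionnaire (section 11.2) tests these elements separately: Q3 asks for the potential risks, Q7 for the urinary symptoms that patients should be warned about, and Q8 for the advice to a patient who cannot pass urine.

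Section 5.2 defines the primary outcome as "the proportion of subjects that correctly respond to individual survey questions concerning the risk of urinary retention" and its symptoms, and adds: "The proportion responding correctly will be tabulated separately for each item in the subject understanding survey instrument". Section 7.2 plans a point estimate and 95% confidence interval per question, the distribution of responses to multiple-choice questions, and the same by subgroup. Its overall summary is the counterpart of the subgroups, not a score per respondent. Section 7.2 then attaches a meaning to the item results: a rate of "at least 80% for each individual question to represent sufficient subject understanding of the risks associated with POTIGA". No result in the protocol combines questions within a respondent.

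**The concern.** A set of item percentages is silent on overlap. When 20% miss each of three questions, these may be the same respondents or largely different ones, and the item tables look identical either way. In the first case four in five respondents hold the whole message; in the second, far fewer may do so.

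The interpretive sentence in section 7.2 passes over this difference. A report could find every urinary-retention item at the benchmark, state that understanding of the risks is sufficient, and be read as saying that about 80% of prescribers know the risk, its symptoms and the action. The report goes to FDA (section 10.4) as an assessment of whether the communication plan worked (section 1), so the reach of that sentence matters even though nothing is formally tested.

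**Working it through.** **Inputs.** Benchmark of 80% per question (section 7.2). About 200 prescribers and 200 pharmacists (Protocol Summary). Three items, Q3, Q7 and Q8 (section 11.2). The correlation between items is not in the documents, so it is assumed and shown as a range.

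**1. The plan's own figure.** Section 8 gives ±5.5 points at 80% and n=200. The usual normal approximation gives 1.96 × √(0.80 × 0.20 / 200) = 0.0554, so the figure reproduces. It is the precision of one question.

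**2. Limits that need no assumption.** Let each of the three items be correct in exactly p = 0.80.
- Lowest joint share: 1 − 3 × (1 − p) = 1 − 3 × 0.20 = 0.40, reached when no respondent misses more than one item.
- Highest joint share: p = 0.80, reached only when the same 20% miss all three.

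**3. Between the limits.** Under independence the joint share is 0.80³ = 0.512, about 102 of 200. For positive dependence I used an equicorrelated latent normal model: joint share = ∫ Φ((a − √ρ·x)/√(1 − ρ))³ φ(x) dx, with a = Φ⁻¹(p).

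| Dependence between items | All three correct, items at 80% | All three correct, items at 90% |
|---|---|---|
| Lower limit | 40% | 70% |
| Independent | 51% | 73% |
| ρ = 0.3 | 57% | 76% |
| ρ = 0.5 | 61% | 78% |
| ρ = 0.7 | 66% | 81% |
| ρ = 0.9 | 72% | 85% |
| Upper limit | 80% | 90% |

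**4. Precision of a joint proportion.** At 51.2% and n=200, 1.96 × √(0.512 × 0.488 / 200) = 0.069. Table 1 of the protocol already lists 7.0 points at 50% and n=200.

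**5. What an 80% joint share would demand.** Under independence each item would need 0.80^(1/3) = 92.8% correct. To guarantee it whatever the dependence, each would need 1 − 0.20/3 = 93.3%.

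**The case against.** The strongest reply is that the plan is coherent as it stands. The benchmark, the primary outcome, the tabulation and the precision calculation all use the single question. The study is declared descriptive, so no decision rule is miscalibrated. Item results are also what is needed to see which message failed to get across. All of this stands, and it is why the item-level primary outcome should stay.

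A second reply is that no section defines understanding as Q3, Q7 and Q8 all correct. That is so. Risk and symptoms come from the objectives, while the action comes from the description of the communication plan. The three-item set is a reasonable reading of those sections, not a definition in the protocol.

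Third, the low figures are not forecasts. The 40% limit needs misses that never overlap, and independence is doubtful for three questions on one topic. Q7 and Q8 allow several responses, so part of the joint knowledge may already sit within an item; the protocol shows no answer key. This limits the size of the point but does not remove it: below 80% is possible under any dependence short of complete overlap.

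An analysis plan that is not shown could add a joint result. It would not by itself alter the interpretation that section 7.2 fixes.

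Three stronger readings are tempting and not supported:
- A reader might infer that the Protocol Summary, which speaks of the "proportion of physicians and pharmacists providing correct responses to a series of questions concerning the risk of urinary retention", sets a respondent-level outcome that sections 5.2 and 7.2 contradict. The phrase is compatible with question-by-question reporting and does not require all answers to be correct together.
- A reader might add the timing and monitoring-group questions (Q12, Q13) to get a larger gap. Neither element appears in the objectives or in the message described in section 1.
- A reader might apply 80% to the joint result. Section 3.3.1 derives the benchmark for individual questions from earlier programmes; step 5 shows how much stricter the joint version would be, and the documents give no basis for it.

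**Conclusion.** The point holds as a matter of interpretation. Section 7.2 draws a broader conclusion than item percentages can carry. With Q3, Q7 and Q8 each at exactly 80%, the share of respondents correct on all three is certain only to lie between 40% and 80%. Values of 51% to 72% correspond to dependence from none to a latent correlation of 0.9.

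The limits rest only on the 80% benchmark and the choice of three items; the intermediate values rest on an assumed correlation. At 90% per item the lower limit rises to 70%, so the issue fades if scores are well above the benchmark. It cannot be concluded that joint knowledge will in fact be far below 80%, only that the planned results could not reveal it. The same holds for pharmacists. This is a worthwhile and cheap improvement.

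**What to change.** 1. Keep the per-question primary outcome and its 80% benchmark. Reword the sentence in section 7.2 so that reaching 80% on a question indicates sufficient understanding of the single message which that question tests.
2. In sections 5.2 and 7.2 add a descriptive result, for prescribers and pharmacists separately: the proportion of respondents with Q3, Q7 and Q8 all correct, with its 95% confidence interval. Do not apply the per-question 80% threshold to it.
3. Base any statement about understanding of the whole message on that joint result.

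The cost is one derived variable and one extra row per group, with no new data. Responses are held by the contract research organization under a numeric subject identifier (section 6). Because section 10.2 keeps individual-level data from the sponsor, the variable should be specified for that organization to derive; it cannot be rebuilt from item tables. The real downside is a headline figure that can be no higher than the lowest of the three items and will usually be less favourable.

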8. PRECISION BY SAMPLE SIZE

If the estimate of the percentage of subjects indicating a correct response to an individual survey question is 80%, then a sample of 200 subjects will provide a margin of error of ± 5.5 percentage points of this estimate with a 95% confidence interval. The margin of error reduces to ± 4.7 percentage points if the sample size increases to 300. Subgroups of the total sample will have smaller numbers of subjects, resulting in larger margins of error and therefore provide estimates with lower precision. The following table indicates the margin of error at the 95% confidence level provided by varying sample sizes and estimates of percentage of subjects indicating a correct response.

Table 1 Sample size and precision estimates

Sample Size	Proportion of Correct Responses to Each Question						
	50	60	70	75	80	85	90
	Precision/ Margin of Error ($\pm\%$) with 95% Confidence Interval						
50	14	14	12	11	10	9.0	8.0
100	10	10	9.0	8.0	8.0	7.0	6.0
150	8.0	8.0	7.3	7.0	6.7	5.7	4.7
200	7.0	7.0	6.5	6.0	5.5	5.0	4.0
250	6.0	6.0	5.6	5.4	4.8	4.6	3.6
300	5.7	5.7	5.3	5.0	4.7	4.0	3.3
350	5.1	5.1	4.9	4.4	4.3	3.9	3.1
400	5.0	4.8	4.5	4.3	4.0	3.5	3.0
450	4.7	4.4	4.2	3.9	3.8	3.2	2.7
500	4.4	4.2	4.0	3.8	3.6	3.2	2.6

9. STUDY LIMITATIONS

There are some limitations inherent in the study design. The sample may not be fully representative of prescribers and pharmacists typically prescribing/dispensing POTIGA. However, this limitation will be addressed to the extent possible via recruitment across many geographical regions recruiting a demographically diverse sample. This study aims to limit this potential bias by accessing HCPs via one of the largest online databases of healthcare professionals in the US rather than targeting high POTIGA prescribing physicians or those known to GSK through previous collaborations or participation in clinical studies.

Since this is an online survey, we cannot detect whether or not HCPs attempt to utilize any reference materials while taking the survey. They will not be provided with any reference materials.

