3. INVESTIGATION PLAN

3.1. Study Design

This study is sponsored by GlaxoSmithKline (GSK), and will be conducted by Concentrics Research LLC, a contract research organization, on behalf of GSK.

This is a cross-sectional study of individuals prescribing POTIGA or dispensing AEDs.

Physicians and pharmacists will be recruited using a multi-modal approach:

1. Telephone
2. Email
3. Fax

Screening interviews will take place via telephone, email or fax using a standardized screening questionnaire to assess whether the physician or pharmacist is eligible for and interested in participating in the study. Also, demographic information including clinical specialty and geographic location will be collected at screening.

Following recruitment, physicians' and pharmacists' understanding of the risk of urinary retention and the symptoms of acute urinary retention with POTIGA products will be evaluated using an online survey or the same survey instrument delivered during a telephone interview. If the healthcare provider (HCP) qualifies and is interested in participating, the survey recruiter will schedule an appointment for the interview if the HCP states a preference for the telephone survey, or will send an email including a link to the online survey with their unique passcode. The telephone option will be made available to accommodate individuals who would prefer a telephone call to participate in the survey. It is estimated that approximately 85% will complete the internet survey and the remaining 15% will complete the survey via telephone interview. HCPs will be allowed to respond throughout the entire data collection period, and non-responders will receive up to 5 follow-up messages (sent either via email or phone call) to remind them to participate in the survey.

All physicians and pharmacists will be asked to re-confirm their clinical specialty at the start of the interview (whether online or via telephone). Prescribing physicians (e.g. neurologists, neurosurgeons, epileptologists) will be asked medications prescribed again as well, and pharmacists will similarly be asked to confirm medications dispensed again. Any prescribing physician or pharmacist will be excluded from the survey if he/she gives an answer to these screening questions that would be inconsistent with an answer provided previously during the telephone screening and would also meet an exclusion criteria.

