We would also like to confirm that you are the [INSERT: physician/pharmacist] on record for this survey. Please select one of the following options:

- 1. I affirm that I am the same [INSERT: physician/pharmacist] who was screened and sent the survey passcode. [INSERT NAME]
- 2. I am not [INSERT NAME], but I work in this [INSERT: physician's office/pharmacy].

IF PUNCH 1 (SAME PHYSICIAN/PHARMACIST), CONTINUE.

IF PUNCH 2 (NOT PHYSICIAN OR PHARMACIST, BUT WORK IN SAME OFFICE/PHARMACY), SHOW SCREEN WITH MESSAGE: 'THANK YOU FOR YOUR TIME. UNFORTUNATELY, ONLY THE HEALTHCARE PROVIDER ON RECORD MAY PARTICIPATE IN THIS STUDY. IF YOU BELIEVE YOU HAVE RECEIVED THIS MESSAGE IN ERROR, PLEASE CONTACT [INSERT NAME & PHONE #] FOR FURTHER INSTRUCTIONS.' DO NOT ALLOW SUBJECT TO CONTINUE.

Survey

The following questions are being asked about your understanding of the prescribing information and practices related only to POTIGA (ezogabine). Please respond only about this medication, based on what you know at this time.

Please take your time and read each question carefully.

Please do not guess - if you do not know the answer, please just select 'I don't know'.

1. According to U.S. prescribing information, what is the FDA-approved indication for POTIGA? (Please select all that apply)

ALLOW MULTIPLE RESPONSES, EXCEPT PUNCH 4 OR 5.

Migraine	1
Partial-onset seizures	2
Generalized tonic clonic seizures	3
None of the above	4
I don't know	5

2. True or False: According to U.S. prescribing information, POTIGA can be used as monotherapy.

ALLOW ONE RESPONSE.

True	1
False	2
I don't know	3

3. According to U.S. prescribing information, which of the following are potential risks associated with POTIGA? (Please select all that apply)

ALLOW MULTIPLE RESPONSES, EXCEPT PUNCH 5 OR 6.

Urinary retention	1
Pancreatitis	2
Ischemic colitis	3
I don't know	4

4. According to U.S. prescribing information, what is the maximum recommended daily maintenance dose of POTIGA for the General Population?

ALLOW MULTIPLE RESPONSES, EXCEPT PUNCH 5 OR 6.

600mg	1
900mg	2
1200mg	3
2000mg	4
None of the above	5
I don't know	6

5. According to U.S. prescribing information, which of the following statements, if any, is true? (Please select all that apply)

ALLOW MULTIPLE RESPONSES, EXCEPT PUNCH 5 OR 6.

The oldest age at which POTIGA can be used is 65	1
There are no lower age limits for POTIGA	2
The youngest age at which POTIGA can be used is 12	3
The youngest age at which POTIGA can be used is 18	4

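### Section 9 concedes undetectable look-up but names neither its upward direction nor the telephone mode, and no instruction shown tells respondents not to consult references

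*Protocol*

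**What the plan says.** Section 9 (Study Limitations) states "Since this is an online survey, we cannot detect whether or not HCPs attempt to utilize any reference materials while taking the survey". The one mitigation it names follows directly: "They will not be provided with any reference materials".

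Section 3.1 (Study Design) describes two modes, not one: "It is estimated that approximately 85% will complete the internet survey and the remaining 15% will complete the survey via telephone interview". Online respondents work from an emailed link and may respond at any time in the data collection period.

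The survey instructions in Section 11.2 say "Please respond only about this medication, based on what you know at this time" and then "Please do not guess - if you do not know the answer, please just select 'I don't know". They do not mention reference materials. Some stems do point to the label. Q3, the direct urinary-retention item, reads "According to U.S. prescribing information, which of the following are potential risks associated with POTIGA".

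Section 7.2 sets the benchmark of at least 80% correct for each question, for prescribers and for pharmacists. Its list of reporting subgroups does not name survey mode, but the list is introduced as illustrative rather than complete.

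**The concern.** The objectives in Section 2 are about understanding, and Section 1 speaks of whether prescribers and pharmacists can recall the risk. An answer found in the label during the survey measures neither. Physicians and pharmacists have ready access to the label, so not supplying it does little to prevent its use.

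The error is not neutral. A respondent who knows the answer gains nothing by checking, while one who does not know it can move from wrong or don't-know to correct. The proportion correct therefore rises toward the fixed 80% threshold. A larger sample does not reduce this shift, and the 95% confidence interval does not reflect it. Section 9 states the limitation without its direction, and attributes it to the whole study although a telephone mode is planned.

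**Working it through.** **Inputs from the protocol.** Threshold 80% (Section 7.2); about 200 physicians and 200 pharmacists (Protocol Summary); expected split 85% online and 15% telephone (Section 3.1); 95% margin of ±5.5 points at 80% correct with n = 200 (Section 8).

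**Inputs assumed.** Let u be the share of online non-knowers who look the answer up. The documents give no value, so I take 5% to 50%. I also assume that every look-up gives the correct answer and that telephone respondents do not look up.

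**1. The plan's own figure.** 1.96 × √(0.80 × 0.20 / 200) = 5.54 points, which agrees with the stated ±5.5.

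**2. Look-up needed to reach 80%.** With true knowledge p, the observed proportion is p + 0.85 × u × (1 − p). Setting this to 0.80 gives u = (0.80 − p) / [0.85 × (1 − p)]. As a share of all online respondents it is (0.80 − p) / 0.85.

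| True p | Share of online respondents | Share of online non-knowers (u) |
|---|---|---|
| 78% | 0.02/0.85 = 2.4% | 10.7% |
| 75% | 0.05/0.85 = 5.9% | 23.5% |
| 70% | 0.10/0.85 = 11.8% | 39.2% |
| 65% | 0.15/0.85 = 17.6% | 50.4% |
| 60% | 0.20/0.85 = 23.5% | 58.8% |

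In counts, for one group of 200 with p = 75%: 170 are online, of whom 0.25 × 170 = 42.5 do not know the answer. Ten look-ups (10/170 = 5.9%; 10/42.5 = 23.5%) add 10/200 = 5 points.

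**3. Observed result over the assumed range.** At p = 75%, u = 5%, 10%, 20%, 30% and 50% gives 76.1%, 77.1%, 79.3%, 81.4% and 85.6%. At p = 70%, u = 5% to 50% gives 71.3% to 82.8%.

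**4. Stem wording.** Q1, Q2, Q3, Q4, Q5, Q6, Q9 and Q10 refer to the U.S. prescribing information: eight of 13. Six open with the phrase; Q2 and Q10 carry it after a true-or-false lead-in. The urinary or voiding items are Q3, Q7, Q8, Q12 and Q13, and only Q3 carries it.

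**5. Could a comparison by mode show the bias?** At 80% correct, the margin for the difference is 1.96 × √(0.16/n₁ + 0.16/n₂).

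- Per HCP group, 170 online (±6.0) against 30 telephone (±14.3): difference ±15.5 points.
- Both groups pooled, 340 online (±4.3) against 60 telephone (±10.1): difference ±11.0 points.

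A true 75% that reads as 80% implies an online-minus-telephone gap of 0.05/0.85 = 5.9 points, well inside both margins. A true 70% that reads as 80% implies 11.8 points, inside the per-group margin and only just outside the pooled one.

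**The case against.** The strongest reply is that the protocol discloses the limitation and does not leave respondents without guidance. They are told to answer from what they know now and are given a legitimate exit if they do not know. That stands. A reader might infer that respondents get no instruction bearing on this at all; the documents do not support it. What is missing from the text shown is an explicit request not to consult sources. Even that is qualified: respondents sign a Confidentiality and Consent Agreement whose text is not shown, so such a request there cannot be excluded.

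A reader might also infer that the questionnaire invites look-up across the risk items. It does not. Seven of the eight label-referring stems concern indication, monotherapy, dose, age and food, and four of the five urinary items have no such wording.

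A third tempting inference is that leaving survey mode out of Section 7.2 is an analytic defect and that online against telephone would be a sound internal check. The subgroup list is open, and a statistical analysis plan may add mode. Respondents choose their mode, telephone respondents could also look answers up, and step 5 shows that the comparison lacks the precision to settle the matter. A null result could reassure falsely.

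Finally, the size is hypothetical. No look-up rate is given, nothing places true knowledge at 70% or 75%, and the 85% is an advance estimate. This is right, and the figures show only how much look-up would matter if it occurred.

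**Conclusion.** The point holds as a weakly mitigated and incompletely described limitation. It is not a contradiction in the analysis, nor evidence that the results will be wrong. The direction is clear: look-up raises the proportion correct toward the 80% threshold. Under the stated assumptions, look-up by about 6% of online respondents (23.5% of online non-knowers) would turn a true 75% into an observed 80%, a shift close to the ±5.5-point sampling margin. An item with true knowledge further below the threshold needs much more: at 60%, 58.8% of online non-knowers. The concern therefore bites for items a few points short of 80%. The conclusion rests on correct look-ups, none by telephone, and the expected 85/15 split; fewer correct look-ups or a smaller online share would raise the rate needed.

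**What to change.** - **Section 11.2, survey instructions.** Add one line, for example: *Please answer from memory, without consulting the prescribing information, website, letters or other sources.* Use it in both modes, since Section 3.1 requires a common script.
- **Section 9.** Replace the description of the study as online with a statement that undetectable look-up applies mainly to the online respondents (expected about 85%) and would bias the proportion correct upward, toward the 80% threshold.
- **Optional.** Show the urinary-retention items by survey mode, labelled as descriptive, self-selected and too imprecise to confirm or exclude a bias of this size.

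The cost is one sentence in the instrument and one corrected sentence in the protocol, with one extra table column if the optional item is taken up. The new line will not stop a determined respondent and does not make look-up detectable. If fieldwork is already under way, it reaches only later respondents, so the date of the change should be recorded.
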